6.2 DOSE MODIFICATION GUIDELINES

6.2.1 DOSE FREQUENCY AND DOSE LEVEL REDUCTIONS

Subjects enrolled in this protocol will begin treatment at the same carfilzomib dose level, frequency and method as the last dose received on their previous study. Dose levels are as follows:

[figure not shown]
Table 1: Carfilzomib for Injection Dose Levels

Carfilzomib Dose Levels
11 mg/m ²
15 mg/m ²
20 mg/m ²
27 mg/m ²
36 mg/m ² *
45 mg/m ² *
56 mg/m ² *

* Dose level for 30-minute infusion

Dose frequency reductions will be allowed at the discretion of the Investigator in consultation with the Medical Monitor. The dose frequency can be reduced to carfilzomib administration on Days 1, 2, 15, and 16 (eg, every other week dosing) of a 28-day cycle, and continued until conditions in section 3.4 are met.

Dose level reductions, to a minimum dose of $11 \text{ mg}/\text{m}^2$, for toxicity will also be permitted; the Medical Monitor may be consulted as needed. Missed doses of carfilzomib will not be made up. Doses of carfilzomib may be rescheduled by up to 48 hours if the scheduled administration falls upon a holiday. Anticipated delays of a scheduled carfilzomib dose by more than 1 day should be discussed beforehand with the Medical Monitor. A dose reduction guideline diagram is as follows:

6.2.2 DOSE MODIFICATIONS FOR HEMATOLOGIC TOXICITIES

Study drug will be withheld from subjects with:

- Grade 3 neutropenia ($\text{ANC} < 1000/\text{mm}^3$)
- Grade 4 thrombocytopenia with active bleeding

Grade 4 anemia and thrombocytopenia (without active bleeding) do not require the carfilzomib dose to be withheld. However, subjects should receive supportive measures in accordance with institutional guidelines. *For patients with Grade 4 thrombocytopenia without evidence of bleeding, study drug dosing may occur following consultation with the Medical Monitor.*

Subjects with reversible and manageable hematologic toxicity (eg, effects have diminished to baseline or better at the time of the next scheduled treatment) will continue to receive carfilzomib at the same dose level. For the purposes of this study, ‘baseline’ refers to the subject’s status at the start of this Protocol (PX-171-010).

If required by continued or worsening toxicity, dose level and/or frequency reductions will be permitted after discussion with the Medical Monitor. The minimum dose level will be 11 mg/m². Dose reductions below 11 mg/m² will not be permitted. The minimum dose frequency will be carfilzomib administration on Days 1, 2, 15 and 16 (eg, every other week). Less frequent dosing will not be permitted. If toxicity continues, the subject should be removed from the study.

For subjects whose dose level/frequency is reduced due to study drug-related hematologic toxicity, dose level/frequency re-escalation may be considered if the subject tolerates the reduced dose and at the Investigator’s discretion in consultation with the Medical Monitor.

If there is no resolution of toxicity after 2 weeks of withholding treatment (up to 3 weeks for infection treatment), the subject will be withdrawn from the study.

6.2.3 DOSE MODIFICATIONS FOR NON-HEMATOLOGIC TOXICITIES

Study drug should be held for drug-related \geq Grade 3 events until resolution to \leq Grade 1 or return to baseline status. For the purposes of this study, ‘baseline’ refers to the subject’s status at the start of this Protocol (PX-171-010).

After resolution to \leq Grade 1 or return to baseline status of the event, subsequent treatment with carfilzomib may resume at full dose at the Investigator’s discretion.

If required by continued or worsening toxicity, dose level and/or frequency reductions will be permitted after discussion with the Medical Monitor. The minimum dose level will be 11 mg/m². Dose reductions below 11 mg/m² will not be permitted. The minimum dose frequency will be carfilzomib administration on Days 1, 2, 15, and 16 (eg, every other week). Less frequent dosing will not be permitted. If the toxicity continues, the subject should be removed from the study.

For subjects whose dose level/frequency is reduced due to study drug-related toxicity, dose level/frequency re-escalation may be considered if the subject tolerates the reduced regimen and at the Investigator's discretion in consultation with the Medical Monitor.

If there is no resolution of toxicity after 2 weeks of withholding treatment (up to 3 weeks for infection treatment), the subject will be withdrawn from the study.

6.2.3.1 Decreased Creatinine Clearance

Carfilzomib should be held for calculated creatinine clearance (CrCl) < 15 mL/min.

For subjects who enter this study with a CrCl < 15 mL/min, study drug should be held if CrCl drops $\geq 50\%$ from baseline. When the CrCl returns to baseline, carfilzomib treatment should resume at 1 dose level reduction (ie, from 27 to 20 mg/m², from 20 to 15 mg/m², or from 15 to 11 mg/m²). If the CrCl is still $\geq 50\%$ below baseline after 2 weeks the subject should be withdrawn from the study.

Subjects on routine hemodialysis may receive carfilzomib at the same dose as the previous carfilzomib study.

The Cockcroft and Gault formula will be used to calculate the CrCl as follows: Creatinine Clearance = $\{[(140 - \text{age}) \times \text{Mass (kg)}] / [\text{Creatinine (mg/dL)} \times 72]\} \times 0.85$ if female.

Table 2: Dose Adjustment Guideline for Renal Dysfunction

Renal Dysfunction	Recommended Action
Normal to Mild (CrCl > 50 mL/min)	Full dose
Moderate to Severe (CrCl 15–50 mL/min)	Full dose
Upon study entry, CrCl < 15 mL/min and CrCl drops below 50% of baseline	Hold carfilzomib until CrCl returns to baseline; restart at 1 level dose reduction

6.2.3.2 Infections

Subjects with active or suspected infections should have treatment withheld until the infection has resolved and anti-infective treatment has been completed. After the infection has resolved and anti-infective treatment has been completed, treatment may continue at the

original dose. If there is no resolution of the infection after 3 weeks, the subject will be withdrawn from the study.

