6 TREATMENT PROCEDURES

6.1 DRUG PREPARATION AND ADMINISTRATION

6.1.1 CARFILZOMIB DRUG ADMINISTRATION

Carfilzomib for Injection is supplied as a lyophilized parenteral product in single-use vials which, when reconstituted with an appropriate volume of Water for Injection, contains 2 mg/mL of carfilzomib. The product is supplied in labeled carton(s) and is shipped and stored between 2°C–8°C (36°F–46°F). Details of the description, formulation, preparation, storage, and accountability of Carfilzomib for Injection may be found in a separate Pharmacy Manual.

Carfilzomib will be administered IV, using the same method, frequency, and at the same dose level as administered in the last cycle of the subject's previous carfilzomib study; in this study, carfilzomib doses will be administered on Days 1, 2, 8, 9, 15, and 16 of a 28-day cycle (or the same dose level and frequency as administered at the last visit of the prior carfilzomib study) until disease progression or unacceptable toxicity. Each dose will consist of Carfilzomib for Injection administered on an mg/m² basis. Subjects with a body surface area (BSA) > 2.2 m² will receive a dose based upon a 2.2 m² BSA.

Dosing will be continued or modified based upon clinical and laboratory findings.

The dose will be administered at a facility capable of managing hypersensitivity reactions. If a carfilzomib dose is delayed by more than 1 day, it will not be made up.

Subjects should be well hydrated prior to dosing with carfilzomib. Blood chemistries, including creatinine, complete blood counts (CBC), and platelet count must be obtained and reviewed by the Principal Investigator or qualified designee prior to carfilzomib dosing for all treatment cycles, and the values must meet the guidelines below for retreatment.

Electrolyte abnormalities that are clinically significant should be corrected prior to dosing.

Subjects should have a dedicated line for drug administration. Before and after carfilzomib administration, the line must be flushed with 20 mL of normal saline. If a dedicated line is not possible, the existing line must be flushed with a minimum of 20 mL of normal saline before and after carfilzomib administration.

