6.2.3.4 Conditions Not Requiring Dose Reduction

The following conditions are exceptions to the above guidelines. Carfilzomib does not need to be held in the following cases:

- Grade 3 nausea, vomiting, or diarrhea (unless persisting > 3 days with adequate treatment of anti-emetics or anti-diarrheals)
- Grade 3 fatigue (unless persisting for > 14 days)
- Alopecia
- \geq Grade 3 hyperglycemia attributed to dexamethasone

Other exceptions may be discussed with the Medical Monitor on a case-by-case basis.

6.2.4 *MISSED DOSES*

Missed doses will not be replaced during a cycle. If a subject misses greater than 2 doses of any cycle for reasons other than toxicity, the subject will be discontinued.

6.2.5 *CHANGES IN BODY SURFACE AREA*

Dose adjustments do not need to be made for weight gains/losses of $\leq 20\%$. Subjects with a BSA of $> 2.2 \text{ m}^2$ will receive carfilzomib based on 2.2 m^2 BSA.

6.2.6 *OTHER DOSING MODIFICATIONS*

Dose modifications and delays different from those stated in the protocol, for management of toxicities, may be permitted but must be decided jointly by the Principal Investigator and the Medical Monitor or designee.

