6.3 SAFETY GUIDANCE FOR INVESTIGATORS

6.3.1 SAFETY GUIDANCE

Based upon the experience in Phase 1 studies with carfilzomib, the following observations must be noted:

Physicians administering carfilzomib in subjects with compromised renal function should hydrate appropriately and treat according to calculated CrCl, not on serum creatinine. It is recommended that electrolyte abnormalities judged as clinically significant by the Principal Investigator (or qualified designee) be corrected to \leq Grade 1 or baseline. Renal function and serum creatinine should be monitored prior to dosing. Carfilzomib must be held if a subject presents with a CrCl < 15 mL/min with the following exception: for subjects with CrCl < 15 mL/min at study entry, study drug must be held if CrCl drops $\geq 50\%$ from baseline. Subjects who develop an active infection requiring systemic treatment should not be dosed with carfilzomib until the infection has resolved and the treatment course has been completed. Subjects with \geq Grade 3 neutropenia should not be treated with carfilzomib.

Carfilzomib dosing must be held for Grade 4 thrombocytopenia with bleeding. If platelet counts do not recover, the dose of carfilzomib may be reduced or held according to the Dose Reductions/Adjustments rules outlined in [Section 6.2.2](#). For Grade 4 thrombocytopenia without evidence of active bleeding, platelet transfusions may be used per study site policies and at the discretion of the Investigator or treating physician.

Carfilzomib treatment can cause nausea, vomiting, diarrhea, or constipation, sometimes requiring the use of antiemetics or antidiarrheals. Fluid and electrolyte replacement should be administered to prevent dehydration.

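### Protocol Sections 6.2.3.2 and 6.3.1 set different triggers for withholding carfilzomib for infection, so capture of some low-grade infections in the primary safety data can depend on which section a site follows

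*Protocol*

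**What the plan says.** **Infection trigger.** Protocol Section 6.2.3.2, among the dose-modification rules, says: "Subjects with active or suspected infections should have treatment withheld until the infection has resolved and anti-infective treatment has been completed". It sets no condition on grade, relatedness or type of treatment. Section 6.3.1, the safety guidance, says: "Subjects who develop an active infection requiring systemic treatment should not be dosed with carfilzomib until the infection has resolved", and adds that the course of treatment must be finished. Neither section points to the other. The general rule for non-hematologic toxicity in Section 6.2.3 begins "Study drug should be held for drug-related" and applies from Grade 3 upward.

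**Collection of adverse events.** Protocol Section 9.3 lists four classes to be reported: peripheral neuropathy of any grade, Grade 3 and 4 events, serious events, and events of any grade that cause a dose to be missed, reduced or stopped. Protocol Section 10.2.1 and SAP Section 3.1 make the last class part of the primary endpoint, and SAP Section 7.6 repeats it as a focus of the safety analysis. The tables listed in SAP Section 7.6.1 cover events leading to dose reduction and to permanent discontinuation. None covers events leading to a missed dose.

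**Late doses.** Protocol Section 6.1.1: "If a carfilzomib dose is delayed by more than 1 day, it will not be made up". Section 6.2.1: "Doses of carfilzomib may be rescheduled by up to 48 hours if the scheduled administration falls upon a holiday", followed by "Anticipated delays of a scheduled carfilzomib dose by more than 1 day should be discussed beforehand with the Medical Monitor". Section 6.2.4: "If a subject misses greater than 2 doses of any cycle for reasons other than toxicity, the subject will be discontinued".

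**The concern.** In most trials a mild infection is recorded whatever happens to dosing. Here the collection rule is selective: a Grade 1-2 non-serious infection is required on the case report form essentially only through its dosing consequence. The hold rule is then part of how the endpoint is measured. If two sites apply different hold rules to the same infection, one generates a missed dose and a reportable event, and the other generates neither. An event that was never recorded cannot be recovered at analysis.

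Patient protection is also at stake. A site working from Section 6.3.1 alone can dose a subject whom Section 6.2.3.2 holds, without knowing that it has departed from the Protocol. With about 50 centers planned (Protocol Section 3.2), uniform reading of the two sections cannot be assumed.

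**Working it through.** The plan gives no figure to reproduce: about 100 subjects are expected, there is no power calculation, and no hypothesis is tested (Protocol Sections 10.1 and 10.5). The check is a comparison of the rules, followed by simple counting.

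**Step 1. The two triggers, case by case (Grade 1-2, non-serious).**

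| Infection on a dosing day | Section 6.2.3.2 | Section 6.3.1 |
|---|---|---|
| Active, systemic therapy needed | hold | hold |
| Active, treated locally | hold | not named |
| Suspected | hold | not named |

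The general rule in Section 6.2.3 does not settle the last two rows, because it starts at Grade 3.

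**Step 2. From hold to data.** If the dose is held and missed, the infection meets the fourth class in Section 9.3 and enters the primary endpoint component. If the dose is given, the infection meets none of the four classes. Section 9.1 has broader wording about reporting changes in toxicity grade, but the list in Section 9.3 and the visit instructions in Sections 7.1 to 7.7 do not carry it. Hence *essentially only*, not *only*.

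**Step 3. Doses affected.** On the Day 1, 2, 8, 9, 15, 16 schedule, count the scheduled doses inside a hold that begins on a dosing day:

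- 7-day hold: 1 to 2 doses. For example, Days 1-7 contain Days 1 and 2; Days 16-22 contain only Day 16.
- 14-day hold: 2 to 4 doses. Days 1-14 contain Days 1, 2, 8 and 9.
- 21-day hold: 4 to 6 doses. Days 1-21 contain all six.

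**Step 4. Subjects affected (assumed values only).** Let k of 100 subjects have an infection in the disputed rows as their only potentially qualifying event, and let s be the share of them seen at sites that hold. The count in the component is raised by k × s. With s anywhere from 0 to 1, k = 5, 10 or 20 gives a spread of 0-5, 0-10 or 0-20 subjects, that is up to 5, 10 or 20 percentage points. These values of k show how the arithmetic works. They are not estimates.

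**Step 5. Late doses.** Read 1 day as 24 hours (an assumption).

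- Up to 24 hours: no conflict.
- Over 24 and up to 48 hours: Section 6.1.1 does not make the dose up. Section 6.2.1 lets it be given if the scheduled day is a holiday, and sends other anticipated delays to the Medical Monitor without saying whether the dose is then given or missed.
- Over 48 hours: the holiday allowance has ended, and only the Medical Monitor sentence still leaves the outcome open.

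Section 6.2.4 acts at more than 2 missed doses. Take a subject with two doses already missed in a cycle for non-toxicity reasons, plus one holiday dose 48 hours late. Counted as missed, 2 + 1 = 3 and the rule applies. Counted as given, 2 + 0 = 2 and it does not.

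**The case against.** **The sections do not strictly contradict each other.** Section 6.3.1 does not say that its case is the only one, and nothing in it permits dosing during a suspected or locally treated infection. A site that follows Section 6.2.3.2 satisfies both. The first sits among the dose-modification rules and the second is guidance, and Section 6.2.6 offers a joint route for departures. This stands as far as it goes: the defect is two thresholds of different scope, not two incompatible orders. It does not remove the point. Section 6.3.1 says its observations must be noted, sends the reader to Section 6.2.2 for platelets but nowhere for infection, and can be followed alone in good faith. Section 6.2.6 covers agreed exceptions and does not define the default.

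**The consequence is small.** Grade 3-4 and serious infections are collected regardless. The study is single-arm and descriptive, and the SAP plans no missed-dose table that could be shifted. The first two statements are right and limit the point. The third describes a gap in the SAP, since the component is listed there as primary.

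**The holiday clause is an exception to a general rule.** That is the natural reading, and a cross-reference would settle most of it. A reader might infer that the clause also changes the adverse-event endpoint. It does not: a holiday is not an adverse event, so the timing of a holiday dose cannot create or remove an event-linked missed dose.

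**Withdrawal timing.** From the words "after 2 weeks of withholding treatment (up to 3 weeks for infection treatment" a reader might infer that Sections 6.2.2 and 6.2.3 run the clock on time off drug, while Section 6.2.3.2 runs it on resolution, so that a subject whose infection clears early but whose treatment course is long is withdrawn under one and kept under the other. The documents do not support this. The full sentence makes failure to resolve the condition, and all three sections allow 3 weeks for infection.

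**Conclusion.** The point holds for the infection trigger. Sections 6.2.3.2 and 6.3.1 differ in scope with no precedence or cross-reference, and because collection is selective, the difference can decide whether a suspected or locally treated Grade 1-2 non-serious infection on a dosing day appears in a primary safety component. The late-dose wording is a secondary, minor point that bears on the missed-dose count behind Section 6.2.4 and on consistent classification.

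The size cannot be estimated, because the documents give neither an infection rate nor the way sites read the two sections. The conclusion assumes that sites record what Section 9.3 and the visit lists ask for; sites that follow the broader wording of Section 9.1 would lose fewer events. It would be too strong to say that the sections order opposite actions, or that the primary safety results are materially distorted.

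**What to change.** 1. **Protocol, infection.** The clinical team reconciles Sections 6.2.3.2 and 6.3.1 into one trigger, states it once, and has the other section refer to it. Which trigger stands is a clinical decision and is not proposed here.
2. **Protocol, late doses (minor).** Reconcile Section 6.1.1 with the holiday and Medical Monitor sentences in Section 6.2.1, so that a late dose is classed as given or missed in the same way for Section 6.2.4. State that classification once, for use in the case report form and the SAP.
3. **SAP Section 7.6.1.** Add a table of treatment-emergent events leading to a missed dose, so that every part of the component in SAP Section 3.1 is tabulated.

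The cost is a protocol clarification, a letter to sites and one more table. No new data are needed. A comparison of results before and after the clarification is not worth adding: in a single-arm rollover study it would be confounded with calendar time and time on treatment.

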6.2.3.3 Congestive Heart Failure

Any subject with symptoms of new or worsening congestive heart failure (CHF), whether or not drug related, must have the dose held until resolution of the CHF. After the CHF has resolved or returned to baseline, treatment may continue at a reduced dose with the approval of the Medical Monitor, or the subject may be withdrawn from the study. If there is no resolution of CHF after 2 weeks, the subject will be withdrawn from the study.

6.2.3.4 Conditions Not Requiring Dose Reduction

The following conditions are exceptions to the above guidelines. Carfilzomib does not need to be held in the following cases:

- Grade 3 nausea, vomiting, or diarrhea (unless persisting > 3 days with adequate treatment of anti-emetics or anti-diarrheals)
- Grade 3 fatigue (unless persisting for > 14 days)
- Alopecia
- \geq Grade 3 hyperglycemia attributed to dexamethasone

Other exceptions may be discussed with the Medical Monitor on a case-by-case basis.

6.2.4 *MISSED DOSES*

Missed doses will not be replaced during a cycle. If a subject misses greater than 2 doses of any cycle for reasons other than toxicity, the subject will be discontinued.

6.2.5 *CHANGES IN BODY SURFACE AREA*

Dose adjustments do not need to be made for weight gains/losses of $\leq 20\%$. Subjects with a BSA of $> 2.2 \text{ m}^2$ will receive carfilzomib based on 2.2 m^2 BSA.

6.2.6 *OTHER DOSING MODIFICATIONS*

Dose modifications and delays different from those stated in the protocol, for management of toxicities, may be permitted but must be decided jointly by the Principal Investigator and the Medical Monitor or designee.

6.2.7 DOSE ESCALATION RULES

Dose escalations beyond the original dose level up to the maximum tolerated dose established in primary carfilzomib studies may be permitted following discussion with the Medical Monitor.

